There will be no “cold-contact” of patients. The RAs will obtain permission from physicians to contact their patients. The RAs will contact the patient and they will be scheduled for an in-person interview. At time of scheduling, RAs will mail or email the consent document to the scheduled patient. The RA will then follow up with the scheduled individual to review the consent over the phone and ask questions about asthma history. The patient should have an interview scheduled within four weeks of the phone consent. Data will be recorded in the patient record. If the patient does not come in for the study visit or for rescheduled visits, the data collected over the phone will be destroyed. RAs will try to reschedule patient interviews up to 5 times, depending on the patient, before destroying the data collected during the phone consent process.

RAs will obtain consent and administer the interview in a space that safeguards confidentiality. Based on preliminary data, we expect a distribution of participants well-balanced by obesity status and by age of asthma onset (early vs. late). We will recruit both obese and non-obese subjects. Obesity is defined as having a body mass index greater than or equal to 30 kg/m². However, we will monitor these parameters during recruitment and conduct purposeful sampling if unbalances are identified.

Acute Care Episodes: We will also interview participants (<30 minutes) and collect blood samples within 24 hours of admission when they have asthma exacerbations resulting in hospitalization at participating sites. There is a limit of one hospitalization interview within a 12 month period. The purpose is to determine whether L-arginine/ADMA ratios and arginase levels fall disproportionately among obese patients with late onset asthma during exacerbations. We will determine when hospitalizations occur by daily electronic queries of the hospitals’ registration systems.

 Mount Sinai	Protocol Name:	Obesity and Asthma: Unveiling Metabolic and Behavioural Pathways
	Principal Investigator:	[name], DrPH
	Primary Contact Name/Contact Info:	[name] / [contact] / [contact]
	Date Revised:	1/25/21
	Study Number:	STUDY-16-00079

For all interviews, acute and non-acute subjects will not sign the consent form unless they are comfortable with the research. Subjects can take as much time as they deem necessary to review the consent form and ask questions.

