The primary asthma morbidity outcomes will be FEV1 and control (ACQ scores); the primary measure of NO metabolism will be L-arginine/ADMA ratio. All analyses will compare four groups: 1) obese with late onset asthma; 2) obese with early onset asthma; 3) non-obese with late onset asthma; and 4) non-obese with early onset asthma. First, we will compare the levels of plasma L-arginine, ADMA, L-arginine/ADMA ratios, and arginase among these groups, at each time point using the Kruskal-Wallis test. The Wilcoxon signed-rank test will be used to compare levels of NO metabolism biomarkers in periods without vs. during asthma attacks. The analysis will involve longitudinal assessment of asthma morbidity measures across four time points (0, 6, 12, and 18 months). We hypothesize that both time-varying covariates (e.g., NO metabolism biomarkers) assessed at the four time points and time-invariant covariates (e.g., early vs. late asthma onset) will predict asthma morbidity assessed at these time points (Figure 1). We also hypothesize potential lagged effects of covariates at earlier time points. As a first step, we will identify the measurement model for the latent variables at each time point using confirmatory factor analysis. Specifically, we will create latent variables representing random effects intercepts and slopes for NO metabolism (NOt0, NOt6, NOt12 and NOt18; where t0 represents baseline NO metabolism biomarkers) and asthma morbidity measures (AMt0, AMt6, AMt12 and AMt18; e.g., FEV1 at baseline, 6, 12, and 18 months). We will estimate slope and intercept parameters using a Weighted Least Squares Mean-Variance adjusted (WLSMV) estimator, which provides robust estimates for complex models with modest sample sizes and can be employed with dichotomous, ordinal, and/or continuous endogenous variables. We will test this measurement model for absolute fit using Chi-square and RMSEA statistics. In addition, we will consider adjusting the model based on modification indices to improve the overall fit.

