Next, an overall unconditional model will be fitted to identify the growth trajectory across time. To that end, we will fit a growth function for NO metabolic biomarkers and asthma morbidity (e.g., FEV1) using linear, quadratic, and unstructured models. Relative model fit will be evaluated based on various indices of exact and close fit:  $\chi^2$  (>.05), the comparative fit index (CFI>.97), the Tucker-Lewis fit index (TLI>.97), the root mean squared error of approximation (RMSEA<.05), and the weighted root mean square residual when using WLSMV (WRMR<.90). The most parsimonious model with the best fit will be retained. Finally, we will fit the full structural model, including the hypothesized relationships. For example, obesity and age of onset will be included as a predictor of NO metabolism-related pathways as well as asthma morbidity. Because we hypothesize that NO metabolism-related pathways are primarily important for obese patients with late onset asthma, we will include an interaction term between obesity and age of asthma onset. The model will also control for sex, age, comorbidities (including OSA), depression, allergic sensitization, and other key baseline covariates. To address the possible mediational effects of NO metabolism-related pathways, we will fit models to estimate both direct and indirect effects, first separately, and then combined. Lagged effects of the time- varying predictors, as well as the effects of the latent growth variables themselves (intercept, slope, and their random effects) will be evaluated as potential mediators (i.e., NO metabolism biomarkers) of the effects of obesity and age of onset on asthma morbidity. We will also be able to compare models of complete vs. partial mediation by comparing constrained models (direct effects constrained to zero) with unconstrained models that allow for partial mediation. Relative fit, as well as estimates of effect size will be calculated, along with Sobel tests and Monte Carlo confidence intervals to evaluate the mediational hypotheses. As indicated above, the interrelationships between gender, obesity, and asthma morbidity is complex, thus, we will explore the potential modifying effects of gender. We will also conduct sensitivity analyses in which we test different thresholds for the definition of good medication adherence (≥70%, 60%, 50%). Once the final model is fitted, we will repeat the analyses freeing the parameters to differ by gender. Comparing these models to a model in which the differential effects of gender are constrained will provide valuable insight into the possible role of

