
gender in the hypothesized effects.

[figure not shown]
**Note:** In addition to data from the 4 scheduled time points, we will also obtain data when patients have asthma exacerbations. Because LGCM is limited in its ability to model effects in which time points are not common throughout patients (as anticipated for exacerbation data), we will use more flexible hierarchical growth models (e.g., linear mixed models or generalized linear mixed models) as needed to explore these data points.

**Aim 2.** Evaluate the interrelation between obesity- and asthma-related illness beliefs, and the impact of cognitive function, on patients' management of these conditions over time: For asthma, we will compare electronic (primary outcome) and self-reported (secondary outcome) adherence to medications according to obesity/age of onset categories using a chi-square test. For obesity, primary outcomes will be the Connor Diet Habit Survey scores for diet and accelerometer data for exercise. Secondary analyses will assess other SMB.

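### The hospitalisation samples are meant to show a disproportionate biomarker fall in obese late-onset patients, but the SAP specifies no between-group comparison of the fall

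*SAP*

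**What the plan says.** Protocol section 3a, under Acute Care Episodes, provides for an interview and a blood sample within 24 hours of admission for an asthma exacerbation. It gives one reason: "The purpose is to determine whether L-arginine/ADMA ratios and arginase levels fall disproportionately among obese patients with late onset asthma during exacerbations". It adds: "There is a limit of one hospitalization interview within a 12 month period".

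The SAP touches these data, or the same biomarkers, in four places:

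- **Aim 1, attack against no attack:** "The Wilcoxon signed-rank test will be used to compare levels of NO metabolism biomarkers in periods without vs. during asthma attacks".
- **Aim 1, between groups:** plasma L-arginine, ADMA, their ratio and arginase are compared "among these groups, at each time point using the Kruskal-Wallis test". A general statement reads "All analyses will compare four groups: 1) obese with late onset asthma; 2) obese with early onset asthma", and goes on to list the two non-obese groups.
- **Aim 1, structural model:** "we will include an interaction term between obesity and age of asthma onset". This sits in the latent growth curve model (LGCM) for the scheduled visits at 0, 6, 12 and 18 months.
- **Note at the end of Aim 1:** because the LGCM handles irregular time points poorly, "we will use more flexible hierarchical growth models (e.g., linear mixed models or generalized linear mixed models) as needed to explore these data points".

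The Power Calculation paragraph covers the LGCMs for Aims 1 and 2. It does not cover the exacerbation comparison.

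**The concern.** A disproportionate fall means that the change from stable state to attack is larger in one group than in the others. The quantity of interest is therefore a difference between groups in a within-patient change. The signed-rank test addresses the change alone. Pooled over groups, it asks whether levels move during attacks. Run inside one group, it asks the same of that group. In neither form does it produce an estimate or a test of the difference.

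At stake is the only reason the protocol gives for interviewing and bleeding patients within a day of admission. A significant signed-rank result could be reported beside the stated purpose although it says nothing about disproportion. Conversely, a fall confined to obese late-onset patients could be diluted in a pooled test and missed.

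**Working it through.** **Matching each planned analysis to the question.** The question needs group × attack state.

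| Planned analysis | What it compares | Tests the difference in fall? |
|---|---|---|
| Signed-rank, Aim 1 | attack with no attack, within patient | No |
| Kruskal-Wallis, Aim 1 | levels between groups at a time point | No; levels at an attack mix prior differences with the fall |
| Obesity × onset term, LGCM | groups across scheduled visits | No; attack state is not in the model |
| Mixed models, Note | not specified | Could, but no outcome, fixed effects or contrast is given |

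**Inputs for an illustration.** The documents state no event count, SD, effect size or power for this comparison, so there is no figure to reproduce. From the SAP: N = 400, four groups, alpha 0.05 (taken as two-sided). Assumed: equal groups, one stable/attack pair per hospitalised patient, normal paired changes with SD 1, and 5%, 10%, 20% or 30% of patients hospitalised (20, 40, 80 or 120 pairs).

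**Does the signed-rank test answer the question?** Simulation with 2,000 studies per scenario. The between-group test is a Mann-Whitney test of the paired change, obese late-onset against the rest. The table shows the percentage of studies with p < 0.05.

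| Scenario | Pairs | Pooled signed-rank | Between-group test of change |
|---|---|---|---|
| Equal 0.5 SD fall in all groups | 20 | 56% | 4% |
| Equal 0.5 SD fall in all groups | 40 | 86% | 4% |
| Equal 0.5 SD fall in all groups | 80 | 99% | 6% |
| 1 SD fall in obese late-onset only | 40 | 26% | 72% |

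With no disproportion the signed-rank test is usually significant, as it should be for the question it asks. With a fall in the target group only, at 40 pairs, it usually is not.

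**What the right contrast can detect.** Smallest effect with 80% power = (1.960 + 0.842) × SE, by normal approximation. With n pairs in total and n/4 per group:

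- pooled fall: SE = √(1/n)
- obese late-onset against the other three combined: SE = √(4/n + 4/(3n))
- obese late-onset against one comparator: SE = √(4/n + 4/n) = √(8/n)

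| Pairs | Pooled fall (SD) | Against three combined (SD) | Against one comparator (SD) |
|---|---|---|---|
| 20 | 0.63 | 1.45 | 1.77 |
| 40 | 0.44 | 1.02 | 1.25 |
| 80 | 0.31 | 0.72 | 0.89 |
| 120 | 0.26 | 0.59 | 0.72 |

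For 40 pairs against one comparator: 2.802 × √(8/40) = 2.802 × 0.447 = 1.25. The ratios to the pooled test are fixed, at √(16/3) = 2.31 and √8 = 2.83. With about 5 pairs per group the normal approximation is optimistic.

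**Repeat pairs.** Protocol section 8 caps observational payments at $380. Four scheduled interviews at $70 give $280, which leaves $100, or two hospital interviews at $50. One patient can therefore contribute two attack samples. The SAP does not say how these enter the signed-rank test, which assumes independent pairs.

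**The case against.** The strongest reply is that the SAP already holds the means. The Note plans mixed models for exactly these data, and Aim 1 says that all its analyses compare the four groups. Read together, these could yield a mixed model with group as a factor, which would also accommodate repeat admissions. This part stands: it would be wrong to say that the plan cannot address disproportion. What is missing is the commitment. The models are optional and exploratory, and no interaction or contrast is written down.

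A reader might go further and infer that the SAP will run the signed-rank test separately in each group, and so manufacture an effect seen only in obese late-onset patients whenever they are hospitalised more often. The documents do not support that. They do not say that the test is run by group, or that a significant result in one group and not in another will be read as disproportion. Nor does the pattern follow in general. With equal true falls of 0.8 to 1.0 SD and 12 obese late-onset pairs, significance in that group alone is common if each comparator has exactly 5 pairs, because the smallest possible two-sided p is then 2/2⁵ = 0.0625. With 8 pairs per comparator it occurs in about 5–12% of studies, and with a 15/10/10/10 split in about 1–6%. No hospitalisation rate is given, so none of these splits can be preferred.

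It is also fair to say that Aim 1's primary outcomes and hypotheses rest on the scheduled visits and the LGCM. No primary result depends on the exacerbation data.

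**Conclusion.** The concern holds as a mismatch between a stated purpose and its analysis. The protocol asks a between-group question, the named test is within-patient, and no text in the SAP specifies the group-by-attack-state contrast. This conclusion comes from the wording alone and needs no assumed numbers. The illustration of its size (about 86% against about 4%) rests on 40 pairs, equal groups, normal changes and a common 0.5 SD fall, none of which the documents supply.

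The point should be fixed. It falls short of a must-fix because the exacerbation data are an exploratory component outside the primary models.

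**What to change.** In SAP Aim 1 and its Note, replace the optional wording with a stated analysis of the protocol's purpose:

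- A linear mixed model for the L-arginine/ADMA ratio, and one for arginase, with group, attack state, group × attack state and a patient random intercept. The random intercept also accounts for up to two hospital samples from one patient.
- Transformation only if the distribution calls for it, as the SAP's analysis overview already allows.
- The patient's scheduled-visit samples as the no-attack reference, with the SAP stating which visits are used.
- The difference in fall for obese late-onset against each of the three comparator groups numbered in Aim 1, with confidence intervals. One pooled comparator would not match the Aim, since it could be positive because of the non-obese groups alone.
- The signed-rank test kept as a description of the overall change, with a sentence that separate within-group p-values will not be read as evidence of disproportion.

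The samples and assays are unchanged, so the cost is SAP wording and some programming. The drawback is precision. If few patients are hospitalised, the interaction estimates will have wide intervals, and the report should say so.

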Obesity and Asthma: Unveiling Metabolic and Behavioral Pathways

Statistical Analysis Plan

PI: [name], DrPH

NCT04113746

Document Date: 8-12-2015

**Data Analyses:** We will obtain a HIPAA waiver to use de-identified data to compare non-respondents and those lost to follow-up to study participants by age, gender and ethnicity. **Factor Structure of Measures:** We will examine the factor structure of key measures (e.g., MARS) and the multi-component structure of the IPQ and BMQ. **Measurement Invariance:** We will determine whether the key measures are invariant across language using multiple indicator multiple cause models. We will use the chi-square test, ANOVA, or the Kruskal Wallis test to compare the baseline characteristics of obese vs. non-obese patients with early onset and late onset asthma, as appropriate. **Overview:** We will employ latent growth curve modeling (LGCM) approaches using MPLUS 7.3 software to test Aims 1 and 2 hypotheses. LGCM leverages the analytical power of structural equation modeling (SEM) for the intensive analysis of longitudinal data. Similar to classic SEM, LGCM allows for the examination of complex models including those that posit mediation and moderation, as proposed here. Before conducting analyses, we will examine the distribution of dependent variables and, as appropriate, consider transformations (e.g., log, Box-Cox) to reduce non-normality in continuous variables.

**Aim 1.** Compare the longitudinal relationship between L-arginine/ADMA balance and morbidity (lung function, asthma control, acute resource utilization, and quality of life) between obese adults with late onset asthma vs. (1) obese adults with early onset asthma and non-obese asthmatics with early (2) or late (3) onset disease:

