**Missing Data:** For data missing at random (e.g., data entry errors), we will use multiple imputation methods with PROC MI and PROC MIANALYZE in SAS. For the outcome assessments, we cannot assume data are missing at random, but we will consider pattern-mixture methods to adjust for an occasional missed point in subjects who complete subsequent follow-up. **Power Calculation:** Power calculations for LGCM and sample size based were based on published methods. Effect size in this approach is defined as a null and alternative hypothesis value of the RMSEA index, which we hypothesize to be 0.05 (adequate fit) and 0.03 (good exact fit), respectively. Power in SEM can be conceptualized as a function of sample size and the number of parameters to be estimated in the model, relative to the information provided in the overall variance-covariance matrix of the observed variables. The estimated power is based on a proposed sample size of 400 with an 80% follow-up rate. For Aim 1, the proposed model involves 14 latent variables across all time points, and 34 observed underlying variables, yielding estimated power >0.80 for an average effect of 0.10 with an alpha of 0.05. For the model in Aim 2, there are 13 latent variables (not including the six separate indicators of cognition) and 18 observed variables, yielding >0.80 power for average effects of 0.15. Overall, despite the challenges of estimating *a priori* power for SEM approaches, especially those involving growth models, we believe the proposed study will be adequately powered to address the research aims.

**Aim 3.** Develop and pilot test three theory-based modules that integrate counseling for asthma and obesity to promote better SMB, including self-monitoring, adherence to asthma medications, and lifestyle changes for weight loss: **Overview:** We will script messages aimed to counter beliefs linked to low adherence to asthma and obesity SMB and to support those that promote better SMB. We will incorporate these messages in 3

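### The Aim 1 growth models use WLSMV with no rule for permanent drop-outs, so growth means are biased if leaving depends on earlier outcomes; full-information ML avoids this under MAR

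*SAP*

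**What the plan says.** The SAP overview announces "latent growth curve modeling (LGCM) approaches using MPLUS 7.3 software" for Aims 1 and 2. Under Aim 1 the primary morbidity outcomes are FEV1 and "control (ACQ scores); the primary measure of NO metabolism will be L-arginine/ADMA ratio". The design is a "longitudinal assessment of asthma morbidity measures across four time points (0, 6, 12, and 18 months"). For the growth parameters it says: "We will estimate slope and intercept parameters using a Weighted Least Squares Mean-Variance adjusted (WLSMV) estimator". Two reasons follow: good behaviour of complex models in modest samples, and suitability for dichotomous, ordinal and continuous endogenous variables. The fit criteria include "the weighted root mean square residual when using WLSMV (WRMR<.90"), a conditional wording, but no second estimator is named for these models. The Note after Aim 1 keeps mixed models for the exacerbation data, as needed.

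Under Missing Data, for values missing at random, with data-entry errors as the example, "we will use multiple imputation methods with PROC MI and PROC MIANALYZE in SAS". Outcomes are then set apart: "For the outcome assessments, we cannot assume data are missing at random". The only measure for them is that pattern-mixture methods will be considered for an occasional missed visit in patients who come back. Under Power Calculation: "The estimated power is based on a proposed sample size of 400 with an 80% follow-up rate". Under Data Analyses, patients lost to follow-up are compared with participants on age, gender and ethnicity. Earlier FEV1 and ACQ are not on that list.

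**The concern.** WLSMV fits the model to univariate and pairwise sample statistics. Unless incomplete outcomes are imputed first, each visit's mean comes from those who attended. A leaver's earlier record then does not inform the later mean. If patients who are doing worse tend to leave, later means look too good and the growth curve shows improvement that did not occur.

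This arises even when leaving depends only on values already in the database, which is the case that likelihood methods on all available visits handle. It is therefore separate from the not-at-random worry that the SAP raises itself.

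Nothing in the Missing Data paragraph closes the gap. Imputation is not assigned to outcomes, and the pattern-mixture sentence leaves out patients who go for good, who are the main consequence of 20% loss. A comparison on three demographic variables would not reveal the problem. At stake are the growth means of the primary outcomes and, under added conditions, the group contrasts in change.

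**Working it through.** **The plan's own figure.** Power is defined by RMSEA 0.05 against 0.03 at alpha 0.05. With 80% follow-up, N = 0.80 × 400 = 320. The noncentrality is λ = (N − 1) × df × RMSEA². At N = 320 and df = 99, λ = 319 × 99 × 0.0025 = 78.95 under the null and 319 × 99 × 0.0009 = 28.42 under the alternative. The lower-tail test then has power 0.80. At N = 400 the same power needs df = 71. The SAP gives no df, but 34 observed variables supply 34 × 35 / 2 = 595 variances and covariances, so the stated >0.80 is reproduced for any plausible df. This figure does not bear on the missing-data question.

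**Inputs.** From the SAP: four visits, 400 patients, 20% loss by month 18. Assumed, because the documents give no drop-out mechanism: within-person correlation ρ of 0.5 or 0.7, and odds ratios for leaving of 1.5, 2.0 or 2.5 per SD worse last value.

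**Model.** Y(i,t) = √ρ·u(i) + √(1 − ρ)·e(i,t), with unit variance, higher meaning worse, and true change 0. Leaving follows logit P(leave before t) = a + ln(OR) × Y(i,t−1), with a set to give 20% cumulative loss.

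**Mean change.** Bias in 18-month change, in SD:

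| ρ | OR 1.5 | OR 2.0 | OR 2.5 | ML on same data |
|---|---|---|---|---|
| 0.5 | −0.045 | −0.073 | −0.092 | 0.00 |
| 0.7 | −0.061 | −0.101 | −0.124 | 0.00 |

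Repeat runs agree to within simulation error, so the range is about −0.04 to −0.13 SD. As a check by hand: if leavers' month-18 mean would lie d SD above that of stayers, the available-case bias is −0.20 × d. A bias of −0.10 corresponds to d = 0.10 / 0.20 = 0.50 SD, which is not extreme.

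**An explicit weighted least squares growth fit.** This used available-case means, variances and pairwise correlations, with a small slope variance (0.01), an intercept share of 0.5 to 0.85, and log-odds of 0.5 to 1.5 per SD (odds ratios e^0.5 = 1.65 to e^1.5 = 4.48). The bias was −0.06 to −0.21 SD at 20% loss. It was 0.00 when leaving was unrelated to the outcome. ML was at most 0.002 away from zero throughout.

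**Group contrast in 18-month change (true value 0).** From the growth fit at log-odds 1.0 (OR 2.72) with intercept share 0.7, unless stated:
- Same level and same mechanism: 0.00 SD.
- One group 0.5 SD worse at the start: −0.06 SD.
- Loss of 30% against 17%: −0.09 SD.
- Leaving tied to the outcome in one group only, 20% loss in each: −0.14 SD.

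ML gave 0.00 in all four. In the simpler model, OR 2 against 1 at 20% loss in each group, or OR 2 to 2.5 with 30% loss against OR 1.5 with 17%, gave −0.07 to −0.14 SD. At OR 2 a 0.5 SD level difference alone gives less, −0.02 to −0.03 SD.

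**Biomarker–outcome path.** With a path of 0.2 or 0.4, a 0.3 SD biomarker shift between groups and one mechanism for all, the 18-month coefficient moves by 0.001 to 0.021 over OR 1.5 to 2.5, and by about 0.01 at OR 2. The group difference moves by less than 0.01 SD.

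**Remedies.** Imputing missing outcomes from earlier outcomes before the weighted least squares fit took the bias from −0.14 to 0.00 SD. If leaving depends on the unseen current value, ML keeps −0.03 to −0.08 SD, against −0.09 to −0.21 SD for the available-case fit.

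**The case against.** The strongest reply is that the overall mean slope is not what Aim 1 tests. Aim 1 concerns the relation between L-arginine/ADMA and morbidity across four groups, through paths, an interaction and indirect effects. Under one shared mechanism those paths hardly move and the group contrast bias cancels. This stands. A reader might infer that the key Aim 1 comparison is biased as planned. The documents give no drop-out mechanism, direction or difference between groups, so they support only a conditional statement.

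Model covariates also help. With a covariate explaining 20 to 30% of outcome variance, the mean-change bias at OR 2 shrinks to −0.03 to −0.07 SD, but it does not vanish.

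Other stronger readings fail as well:
- The bias might seem to rival the SAP's average effect of 0.10. That figure sits in a power statement defined by RMSEA and has no SD-of-change unit, so the two cannot be compared.
- WLSMV might seem justified only by categorical variables. The SAP also cites modest samples and explicitly includes continuous variables. Neither reason addresses missing outcomes, however.
- ML might seem to settle the matter. It does so only under missing at random, which the SAP declines to assume for outcomes.
- The biomarkers might seem to be left unimputed too. The SAP treats them partly as time-varying covariates, so its remark on outcome assessments need not cover them.

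It is also fair to say that WLSMV is curable by prior imputation, and that the conditional wording in the fit criteria leaves room for another estimator. The SAP, though, names no other estimator and assigns no imputation to outcomes.

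**Conclusion.** The concern holds in conditional form and should be fixed. WLSMV without a rule for permanent drop-outs leaves the FEV1 and ACQ growth means open to bias of about −0.04 to −0.13 SD in 18-month change at 20% loss. This assumes odds ratios for leaving of 1.5 to 2.5 per SD and within-person correlation of 0.5 to 0.7. If leaving is unrelated to outcomes, the bias is zero.

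Group contrasts are affected, by about −0.05 to −0.14 SD, only if groups differ in level, amount of loss or outcome-dependence. A level difference alone can give less. Biomarker–outcome paths are little affected (about 0.01) under a shared mechanism. Paths under group-specific mechanisms, and indirect effects, were not evaluated separately.

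The treatment of incomplete cases is a property of the estimator and is not stated in the SAP. The drop-out strengths and correlations are assumptions, not figures from the documents.

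**What to change.** In the SAP, Aim 1, name full-information robust maximum likelihood (MLR), using every enrolled patient's available visits, for models whose outcomes are continuous: FEV1, ACQ, quality of life and the biomarkers. Where categorical indicators require WLSMV, multiply impute incomplete outcomes first, with earlier outcomes in the imputation model.

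Under Missing Data, add a not-at-random sensitivity analysis, for example pattern-mixture, that includes patients who leave for good. This is needed because the SAP itself does not accept missing at random for outcomes.

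The cost is SAP wording and an estimator setting, with no new data. SRMR replaces WRMR in the ML models, so its cut-off must be stated. Imputation and the sensitivity analysis add some work. For imputed WLSMV models the SAP must also say how fit is judged, since PROC MIANALYZE pools estimates and standard errors, not the fit indices used to choose models.
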